Given the documented experiences with medical trauma in this group⁶, we must identify family-informed methods before conducting large-scale work involving non-medically necessary data collection. Therefore, the purpose of this pilot study is to test the feasibility and acceptability of conducting an observational to explore PoFD in children with SNI. The ability to identify the best methods for evaluating potential functional decline (temporary or persistent) in children with SNI will assist in finalizing a study protocol for a planned larger study.

SIGNIFICANCE AND JUSTIFICATION

To our knowledge, this will be the first study to prospectively and quantitatively document item-level post-operative changes in function and quality of life for children with SNI and their caregivers. Expanding upon previous research^{14,15} that has obtained a total score and sub-domain scores of function/health-related quality of life, this work aims to examine more specific, item-level details regarding function pre-

and post-operatively. Additionally, no prior research has investigated potential mechanisms of PoFD, including inflammation, in children SNI.

This pilot study will help refine methods for a planned larger study on this phenomenon. The implications of this future work may significantly improve peri-operative care for children with SNI. Pre-operatively, this could assist clinicians in guiding families through surgical decision-making⁷ and the post-operative recovery trajectory. Post-operatively, our future findings could inform the development of targeted, clinically appropriate, postoperative rehabilitation goals as well as help identify needs for multidisciplinary health and community supports. This work will also set a foundation for research that investigates potential mechanisms for the changes in functional status, if present, which could inform interventions that ameliorate or prevent PoFD. Given the incurable nature of disorders that cause SNI, the impact of SNI and its functional implications on both the child and family is profound²⁶⁻²⁸. This line of work thus has implications to ultimately enhance the quality of life in children with SNI and their families.

STUDY OBJECTIVES

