In this pilot study, we will evaluate the feasibility and acceptability of our protocol to explore the functional post-operative trajectory in a developmentally and neurologically impaired pediatric population. We will evaluate consent rate, protocol delivery and outcome completion, and acceptability. We will also describe common elements of the experience of these children and their families, including information from a functional skills questionnaire, parental descriptions of pre-post abilities, and parental descriptions of their own quality of life. The objectives of our research are:

Primary outcomes

Objective 1: To evaluate the feasibility and acceptability of our study protocol for children and families living with SNI.

To evaluate feasibility we will use the following evaluation points:

1. Consent rate: The overall average consent rate of children/month.
2. Protocol delivery: The percent of on/off protocol children.
3. Outcome completion: The percent of children with complete outcome measures.

To evaluate acceptability, we will conduct end-of-study interviews with caregivers to assess outcomes related to the ease and utility of participating in the study, including our methods of data collection.

Secondary outcomes:

Our secondary aim is to explore patterns of recovery in children with SNI during the peri-operative period. We will assess:

Objective 1: Function in children with SNI, including exploring patterns in specific domains of gain/loss.

Objective 2: Quality of life in children with SNI and their families

Objective 3: Profile of inflammatory biomarkers to compare children's inflammation levels peri-operatively.

HYPOTHESIS

We expect to confirm feasibility and acceptability of conducting peri-operative research in this population, with at least 12 children consented in 1 year and >85% protocol delivery and outcome completion. We anticipate to be able to measure PoFD, quality of life for children and caregivers, and inflammatory biomarkers.

METHODOLOGY

Study Design

This study will use an observational, pre-post intervention design to evaluate our methods of documenting the post-operative functional trajectory and quality of life in children with SNI and their families during the peri-operative period. We will explore the functional abilities and quality of life of children with SNI and their parent/caregivers pre- and post- major orthopaedic surgery, and we will undertake measurements of inflammatory biomarkers

Study Population

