We aim to recruit 12 study participants and 5 control participants for this pilot study, which will be useful to 1) test the feasibility and acceptability of our methods and tools for later use on a larger scale, and 2) allow us to describe patterns in preliminary data to identify early associations that may guide the methodology of a larger study. A sample size of 12 study participants and 5 control participants is likely feasible, as the Orthopedic Clinic sees an average of 50 children for hip/spine surgery each year.

STUDY PROCEDURES

The study will include a total of six timed assessments (**Figure 1**). This includes three primary study assessments to collect functional survey and biomarker data: 1) at baseline (within three months of surgery), 2) 6 weeks post-operatively, and 3) 6 months post-operatively. Additionally, we will conduct three biomarker-specific collections during the time of surgery immediately prior to the initiation of the procedure, 12-24 hours post-operatively, and 1-2 weeks post-operatively, based on the physiology of the sequence of the innate and adaptive immune response systems. Most study assessments will be timed at standard of care visits at the BC Children's Hospital. Each primary study visit will take approximately 25-30 minutes. Total time of participation will be 1.5 – 2 hours. Measures will be taken congruently with standard clinical care data collection where possible to reduce participation burden. Some participants may be recruited exclusively for functional/quality of life data collection while the team awaits approvals for blood collection and storage, to allow for an increased sample size.

Baseline Data Collection

Study participants who have consented will undergo a total of 3 primary study visits and 6 biomarker collections (**Figure 1**). At Study assessment #1, demographic information for the child (including variables such as age, sex, race/ethnicity, primary diagnosis, GMFCS/CFCS/MACS score) and demographic information of the parent/caregiver (age, sex, relationship to child, employment status, household income, race/ethnicity, distance from home to primary medical facility) will be collected. Outcome measures (see below) will also be collected. Baseline data collection aims to capture the initial status of participants before any surgical intervention, providing a reference point for post-operative comparisons.

Outcome Measures

The follow study procedures correspond to our primary aims:

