To assess feasibility, we will evaluate three primary feasibility outcomes at the time of data analysis. We will calculate consent rate, which is the overall average consent rate of children/month; protocol delivery, which is the percent of on/off protocol children; and outcome completion, the percent of children with complete outcome measures.

To assess acceptability, anytime after the 6-week timepoint, we will conduct semi-structured interviews with families to assess their experience in participating in this study. We will also ask families if there were any domains that were not included in our standardized functional/quality of life questionnaire and questions. Parents may select from pre-identified domains as prompts (including pain, energy, and sleep), and may also provide additional insight through open-ended conversation. Interviews will be recorded, transcribed, and analyzed using thematic analysis.

The follow study procedures correspond to our secondary aims:

Our primary tool for this study to measure our outcomes of function and quality of life will be the Caregivers Priorities and Child Health Index of Life with Disabilities (CPCHILD) Questionnaire³⁵, which has

been proved to be both valid and reliable^{35,36}. The CPCHILD Questionnaire is used to assess the effectiveness of interventions aimed at improving and preserving outcomes for children aged 5-18 years old with severe disabilities, based on caregivers' perspectives. This questionnaire includes 37 items collected from the parent/caregiver measured across six domains: Personal Care/Activities of Daily Living; Positioning, Transferring, and Mobility; Comfort and Emotions; Communication and Social Interaction; Health; Child's Overall Quality of Life; with additional sections for Importance of Items to Child's Quality of Life, Facts about the Child, and Facts about the Caregiver. From responses, standardized scores can be retrieved on a scale of 0 to 100 for each domain, as well as a total score, and we will be examining comparisons at the item-level pre/post-operatively.

Parents/caregivers will also be asked to answer two supplemental questions to provide further insight into 1) other areas of function that were not described by CPCHILD and 2) the quality of life of caregivers.

Blood collection of study participants

To collect information regarding the peri-operative inflammatory profile, we will collect blood samples from study participants at all study time points:

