- **Timepoint #1** (pre-operative appointment): during routine care through venipuncture by C&W Lab Technicians. An additional finger prick will be taken by technicians (non-routine).
- **Timepoint #2** (surgery): prior to incision through peripheral venous line by OR staff
- **Timepoint #3** (12-24 hours post-op): by bedside nurses in T6 or PICU
- **Timepoint #4** (1-2 weeks post-op)
 - Hip patients: non-routine collection by C&W Lab
 - Spine patients: by bedside nurses in T6
- **Timepoint #5** (6 weeks post-op): non-routine by C&W Lab
- **Timepoint #6** (6 months post-op): non-routine by C&W Lab

Participants may choose not to provide their blood samples and remain a participant for our functional questionnaire and quality of life-related data collection. Analysis of blood will be done in collaboration with the Core Facility for Neurology Biomarker Innovation/[name] Laboratory.

A 3 mL aliquot of the child's blood will be set aside for our study. This blood will be transferred to the appropriate collection tubes (heparin coated) to prevent clotting and will be transported to the BC Children's Hospital BioBank for storage.

A lancing device will be used for finger capillary sampling to collect 50uL of blood from the child. The blood sample will be immediately collected following puncture using capillary tubes and transferred into pre-labeled collection tubes (heparin coated to prevent clotting) and mixed to ensure the sample remains homogeneous. After collection, the sample will be stored at -80 C at the BC Children's Hospital BioBank.

Blood collection of control participants

Control participants will only have their blood drawn at three timpoints. Relative to study participants, blood samples will be collected from controls at:

- **Timepoint #2** (surgery): prior to incision through peripheral venous line by OR staff
- **Timepoint #3** (12-24 hours post-op): through routine venipuncture in T6
- **Timepoint #6** (6 months post-op): non routine bloodwork by C&W lab

At the conclusion of data collection, all blood samples will be transported to the UBC [name] Laboratory (coordinated by the BC Children's Hospital BioBank).

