
With respect to statistical analysis of our control group, our primary analysis will involve a group comparison at each timepoint to assess whether, and to what extent, any biomarkers are altered (increased or decreased) in children with SNI compared to our controls. Given the large biomarker panel (approximately 120 biomarkers), data visualization using volcano plots will be employed. Multiple comparison adjustments will be applied using the false discovery rate (FDR) correction method (Benjamini-Hochberg). Biomarker significance will be determined based on effect size thresholds, specifically log2(fold change), with a significance level set at 5% (Type I error). Additionally, associations between biomarkers and study variables (e.g., age, sex) will be explored using Wilcoxon rank-sum tests.

Outcomes

The following outcomes will be utilized to deem our study feasible and acceptable:

Feasibility:

1. Consent rate: An average consent rate of 2-3 children/month
2. Protocol delivery: The protocol can be implemented with >85% protocol delivery.
3. Outcome completion: >85% of outcomes will be complete and measured as scheduled.

Acceptability:

4. General positive report on participation based on semi-structured interview

Secondary outcomes; we will explore pre- and post-operative data to describe patterns in:

1. Function of the child, as scored on the CPCHILD;
2. Quality of life of caregiver, as described by supplemental question;
3. Inflammatory profile of child

DATA STORAGE

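### Does it matter that the acceptability interview is called end-of-study in one section and allowed from week 6 in another?

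*Protocol*

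**What the plan says.** Acceptability belongs to the primary objective, and the protocol gives the interview's timing twice. Under Study Objectives (Primary outcomes): "we will conduct end-of-study interviews with caregivers to assess outcomes related to the ease and utility". Under Outcome Measures: "anytime after the 6-week timepoint, we will conduct semi-structured interviews with families", with no latest time.

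Study Procedures sets three primary assessments: baseline, 6 weeks and 6 months. On the number of contacts it says: "Study participants who have consented will undergo a total of 3 primary study visits and 6 biomarker collections". The final blood timepoint is listed as "6 months post-op): non-routine by C&W Lab". Blood is not collected from every child. Families may decline it and stay in the study, and Study Procedures adds: "Some participants may be recruited exclusively for functional/quality of life data collection while the team awaits approvals for blood collection and storage".

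The Outcomes list opens with "The following outcomes will be utilized to deem our study feasible and acceptable", and its acceptability entry is "General positive report on participation based on semi-structured interview". Data Analysis says that the interviews will be analysed thematically. Neither of these two places gives a time for the interview.

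**The concern.** The two statements of timing are not equivalent. An interview at week 8, say, complies with Outcome Measures but is not an end-of-study interview. Staff working from Outcome Measures alone could interview any number of the 12 families before the 6-month visit.

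A caregiver interviewed early cannot comment on the 6-month return visit, on the final non-routine draw, or on what it was like to stay to the end. That interview would still feed the single overall acceptability judgement. The introduction says that the pilot "will assist in finalizing a study protocol for a planned larger study", and it explains that family-informed methods are needed before larger work with data collection that is not medically necessary. A non-routine draw at 6 months is data collection of that sort. The worry is that the primary acceptability conclusion would rest on families with unequal experience of the protocol, and that the plan would not show which families those were.

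**Working it through.** The protocol states no statistical figure on this point, so there is none to reproduce. The check compares the two texts and counts scheduled contacts.

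**Can both statements be met?** Yes. Outcome Measures sets an earliest time and Study Objectives names the end of the study. An interview after the 6-month visit satisfies both. The difference is only that Outcome Measures also permits earlier interviews.

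**What has a family experienced soon after week 6?** Inputs are the assessment schedule in Study Procedures and the list under Blood collection of study participants.

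- Primary visits: baseline and 6 weeks, so 2 of 3.
- Blood collections, if given at every timepoint: #1 to #5, so 5 of 6.
- Post-operative draws labelled non-routine by C&W Lab: hip patients have #4, #5 and #6, of which 2 of 3 come first; spine patients have #5 and #6, of which 1 of 2 comes first.
- The finger prick at #1 is also labelled non-routine. Counting it gives 3 of 4 for hip patients and 2 of 3 for spine patients.
- Families not giving blood: the only difference is 2 of 3 against 3 of 3 visits.

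**Is any kind of procedure missed?** By week 6 a family has completed the questionnaires twice. A family giving blood has also met the routine venipuncture, the finger prick, the pre-incision sample, the 12-24 hour sample, the 1-2 week sample and a non-routine C&W Lab draw. The 6-month visit repeats the content of the 6-week visit: questionnaires, plus a non-routine C&W Lab draw. An early interview misses one further occasion, not a new type of burden.

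**Would loss between week 6 and month 6 go unseen?** No. Study Objectives defines outcome completion as the percentage of children with complete measures, and Outcomes sets the bar at more than 85%. Counted by child, 11/12 = 91.7% passes and 10/12 = 83.3% fails. On that count, two children without a 6-month assessment would already miss the criterion. The Outcomes wording could instead be read as a percentage of outcomes, which is more forgiving, but the missing assessments would still be counted.

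**What would a strict end-of-study rule cost?** Taking 6 months as 26 weeks, the early window is 26 − 6 = 20 weeks. Recall of the early visits would lengthen by up to about that much compared with an interview at week 6. Families who leave within the window might never be interviewed, and their views are among the most informative about acceptability.

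**The case for a change.** The strongest case for a change is that this is not a detail left for a statistical analysis plan. The protocol itself fixes the timing twice, differently, for part of its primary objective. The interview is meant to cover the methods of data collection, and the 6-month draw is one of the non-routine procedures whose acceptability the pilot wants to learn about. Harmonising the text would cost almost nothing. If early interviews are intended, to limit burden or to reach families who leave, the protocol does not say so.

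Much of this stands. The sentences do differ, no visible text reconciles them, and an early interview cannot describe the 6-month visit. Caregivers' views on staying to the end are also not captured by a completion percentage.

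What does not follow is that the acceptability conclusion would be unsound. The missed visit resembles one already experienced, and no direction of bias can be argued from the text. Reporting early and late interviews separately would split 12 families in a thematic analysis that has no score or cut-off, and it would change no result. Nothing makes the Study Objectives wording the controlling one, since Outcome Measures is the operational section. Moving every interview to after 6 months exchanges one limitation for another.

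**Conclusion.** No change to the plan is called for. The inconsistency is genuine but clerical, and following Outcome Measures as written still gives a sound acceptability assessment. At most, an early interview lacks 1 of 3 primary visits and, for families giving blood, 1 of 6 collections. Both are of a kind the family already knows. No sample size, error rate or numeric criterion is affected.

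This rests on three assumptions. First, the 6-month contact is in substance the same as the 6-week contact, as the schedule indicates. Second, whoever analyses the transcripts will know from the interview date which visits each family had completed, and will read the comments accordingly, as is ordinary practice in thematic work. Third, Figure 1, which is not shown, does not contradict the text. The number of early interviews is not fixed by the protocol and could be anything from 0 to 12 of 12. The conclusion holds across that range, because even if all 12 were early, each family would have met every type of study procedure that applies to it. The point concerns only the families of children with severe neurological impairment, since controls contribute demographics and blood samples alone.

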Children undergoing major surgical interventions are at risk of developing acute onset and persistent postoperative functional decline (PoFD)⁵, regardless of their pre-existing cognitive state. While evidence for PoFD exists, it has predominantly been reported in the frail elderly or focused on children without SNI⁶⁻¹¹. To explore this phenomenon more systematically in children with SNI, we conducted qualitative interviews with 12 caregivers to investigate prolonged PoFD. Based on retrospective recall, 80% of caregivers reported unexpected, long-term PoFD in their children¹³. The changes occurred across a wide range of indicators; no two children were alike, making the use of broader categories of functional indicators of change challenging. Two previous studies examining the impact of hip and spinal surgery on health-related quality of life (including functional outcomes)^{14,15} found a decrease in quality of life at six weeks post-surgery, followed by gradual improvement at 12 months and significant improvement five years after surgery^{14,15}. However, these studies analyzed broader categories of function, without specific item-level quantification during the perioperative period. Furthermore, no prospective studies have systematically and specifically examined PoFD in a larger cohort of children with SNI.

While there are several factors hypothesized to contribute to PoFD, including prolonged anaesthesia exposure¹⁶⁻¹⁹ and ongoing pain²⁰, emerging evidence suggests that inflammation due to surgery may be a more likely mediator. Surgery triggers a local inflammatory response with the potential to reach the brain²¹⁻²³. Meta-analyses have found that certain inflammatory markers (eg. C-reactive peptide [CRP], interleukin-6) are significantly elevated in elderly patients with PoFD vs those without^{1,2}, and in adult mice, inhibiting inflammatory cytokines attenuates PoFD-related effects on cognition^{3,4}. Children with SNI may be especially susceptible to inflammation-induced PoFD due to their neurological vulnerability and potentially dysregulated immune response⁵. Inflammation due to surgery may thus be a factor which interacts with neuronal processes to possibly contribute to PoFD. However, the perioperative inflammatory profile in children with SNI and its potential connection to PoFD has not yet been systematically studied.

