We aim to recruit 5 control participants specifically for our biomarker analysis (ie. we will only collect demographics and blood samples). The inclusion of this control group allows for a direct comparison of the pre-, peri-, and post-operative inflammatory responses between children with SNI vs neurotypical patients undergoing similar procedures. This is essential for discerning whether any observed altered biomarkers levels specific to children with SNI (ie. and not seen in neurotypical patients), or if they reflect a generalized postoperative inflammatory response. This comparison strengthens the interpretation of our biomarker findings by providing a baseline, which will reduce the risk of misattributing inflammation-related findings solely to the presence of SNI rather than the general surgical response. Additionally, the inclusion of controls improves the clinical relevance of our study, as it will help determine whether children with SNI exhibit exaggerated, prolonged, or distinct inflammatory responses compared to their neurotypical counterparts. These insights will be critical for guiding future research and potential interventions aimed at mitigating PoFD in children with SNI.

Inclusion Criteria

- 1) Neurotypically developing children (GMFCS I and CFCS I)
- 2) Undergoing major orthopaedic surgical management of musculoskeletal pathology (spine or hip; major defined as a greater than or equal to 90 minute procedure with skin-to-skin contact) at the BC Children's Hospital
- 3) Between 5 and 18 years of age at the time of their surgical procedure

Exclusion Criteria

- 1) Non-English-speaking parents/caregivers

Participant Screening and Recruitment

Participants for this study will be recruited in-person through the BC Children's Hospital Orthopaedic Clinics, including the Orthopedic Cerebral Palsy Clinic (CP Clinic) and the Spine Clinic. Study participants

will receive \$100 remuneration for their participation in the study, and control participants will receive \$50 remuneration for their participation.

Participant Screening

1) Screening through standard-of-care clinical visits

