In collaboration with facilities and technologies of the UBC [name] Lab, biospecimens will be analyzed on the Alamar Biosciences ARGO HT platform, a fully automated immunoassay platform designed for Nucleic acid Linked Immuno-Sandwich Assay (NULISA) technology. The NULISA technology is a ligation-based assay which suppresses assay background using a dual capture and release mechanism with oligonucleotide-conjugated antibodies. It is designed to detect proteins across a high dynamic range with high sensitivity through next-generation sequencing of barcoded reporter DNA produced by the assay which also allows high multiplex capability. Analysis will include relative quantitation of a panel of 120 analytes designed to profile major hallmarks of central nervous system diseases (CNS) using the NULISAsq CNS Panel 120 assay. This assay is commercially available from Alamar Biosciences, and has been validated for sensitivity, precision, cross-lot, and cross-machine performance. Validation testing includes dynamic range, specificity, spike recovery, dilution linearity, sensitivity, intra-run, inter-plate, and inter-lot precision and accuracy. Each NULISA assay run contains 4 negative controls (NCs), 3 sample controls, 3 inter-plate controls (IPCs), and up to 86 samples. Each sample is spiked with the same concentration of an internal control (IC) used in the normalization procedure and as a method for assessing the uniformity of the assay run. IPC samples are pooled plasma controls used to normalize samples between experiments and to assess performance of the assay. NC wells are reactions where no sample input is provided and is used to assess limit of detection (LOD) for each target assay and to assess run quality. SC samples are pooled plasma controls from an independent source different from IPCs. SCs are used for calculating intra- and inter-plate coefficient of variation (CV). Specimens are assayed in singlicate in randomized order with no dilution required. Quality control measures, including but not limited to, CV of spiked IC signal across all samples, CV of the total assay signal across all IPCs, Median CV of all IPC targets, and percentage of targets that are detectable, defined as detectable if > 50% samples have signal > limit of detection, are recorded every run. Raw sequencing reads are processed to generate target- and sample-specific counts called NULISA Protein Quantification (NPQ) values. The raw sequencing reads are first normalized to the IC to control for well-to-well variation and then normalized to the median IC-normalized counts for the IPC samples for plate-to-plate variation.

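### The inflammatory-profile outcome is read from a CNS-disease panel, compared by level between groups split on neurological status, so standing differences can be counted as differences in inflammatory response

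*Protocol*

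**What the plan says.** - **Outcome.** Under Study Objectives, secondary Objective 3 is "Profile of inflammatory biomarkers to compare children's inflammation levels peri-operatively". The Outcomes list at the end of Data Analysis repeats it as "Inflammatory profile of child".
- **Assay.** Data Analysis, Blood collection, names a single assay: "relative quantitation of a panel of 120 analytes designed to profile major hallmarks of central nervous system diseases (CNS". No analyte is labelled inflammatory there.
- **Contrast.** The same section makes its primary control-group analysis a "group comparison at each timepoint to assess whether, and to what extent, any biomarkers are altered (increased or decreased) in children with SNI". It adds: "Given the large biomarker panel (approximately 120 biomarkers), data visualization using volcano plots will be employed". Benjamini-Hochberg correction at 5% is applied, with no sub-families defined.
- **Groups.** Study participants are GMFCS and CFCS levels II to V. Controls are level I on both (eligibility criteria).
- **Interpretation.** The control-group justification says of the comparison that "it will help determine whether children with SNI exhibit exaggerated, prolonged, or distinct inflammatory responses compared to their neurotypical counterparts".
- **Samples.** Controls give blood at timepoints #2 (before incision), #3 (12-24 hours) and #6 (6 months). Study participants are also sampled at all three.
- **Background.** The introduction reports that "certain inflammatory markers (eg. C-reactive peptide [CRP], interleukin-6) are significantly elevated in elderly patients with PoFD vs those without".

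**The concern.** The construct is inflammation, the instrument is described as a CNS-disease panel, and the groups are chosen for having or lacking neurological impairment. Analytes that track neurological disease may differ between these groups on any day, with or without surgery. A level comparison after surgery cannot tell such a standing difference from a different reaction to surgery, yet the stated reading is about response.

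The stake is what the pilot hands on. Sample Size Justification says the pilot should identify early associations to guide a larger study, and the control group was added to avoid misattributing findings. For analytes that follow neurological status, a comparison of levels alone can produce that misattribution.

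**Working it through.** The Protocol gives no power, effect size or SD for this comparison, so there is no figure to reproduce.

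**Inputs from the Protocol:** 12 and 5 children; about 120 analytes; 5% level; Benjamini-Hochberg (BH); a pre-incision sample in both groups.

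**Assumed, not in the Protocol:** two-sided tests; a standing difference d of 0.5 to 2 SD; 25% to 75% of analytes carrying it; pre/post correlation 0.6; independent analytes; a two-sample t test in the simulation.

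**Step 1: what each contrast estimates.** Write the post-operative mean in a group as b + r, where b is the standing level and r the response to surgery.
- Level contrast: (b_SNI − b_control) + (r_SNI − r_control).
- Change from pre-incision: r_SNI − r_control.

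If the responses are equal, the level contrast is exactly the standing difference. FDR control does not help, because that difference is real. It is just not a difference in response.

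**Step 2: chance that one such analyte is flagged, unadjusted 5%.** SE in SD units = √(1/12 + 1/5) = √0.2833 = 0.532. Probability ≈ Φ(d/0.532 − 1.96).
- d = 0.5: Φ(−1.02) = 0.154
- d = 1: Φ(−0.08) = 0.468
- d = 1.5: Φ(0.86) = 0.805
- d = 2: Φ(1.80) = 0.964

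Simulated t tests give 0.42, 0.75 and 0.94 at 1, 1.5 and 2 SD.

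**Step 3: mean number of the 120 analytes flagged after BH at one post-operative timepoint** (1,000 runs per cell, identical response in both groups).

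| Share with standing difference | 1 SD | 1.5 SD | 2 SD |
|---|---|---|---|
| 25% | 1.6 | 11.4 | 24.5 |
| 50% | 4.9 | 32.3 | 53.6 |
| 75% | 11.5 | 56.7 | 83.4 |

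On change from pre-incision, the shifted analytes are flagged at about 5% unadjusted. BH flags on average 0.04 to 0.07 of 120.

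**Step 4: what each part of a repair does.** The simulation tests the change contrast, not an analyte list. A list settles which analytes count as inflammatory, but leaves any standing difference in those analytes untouched. The introduction itself raises a possibly dysregulated immune response in these children. Both parts are needed.

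**Step 5: price of the change score.** With equal variances, Var(change)/Var(level) = 2(1 − ρ). This is 0.8 at ρ = 0.6 and exceeds 1 when ρ is below 0.5.

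**The case against.** The strongest reply is that this is detail for an analysis plan. The panel is named and commercial, so its content can be looked up, and an analyte list could be written without altering the Protocol. The Protocol's wording also leaves room for other assays. The comparison at each timepoint includes the pre-incision sample, where a standing difference may show. Part of the stated purpose is to learn whether altered levels are specific to SNI. The listed secondary outcome is descriptive, and the description of patterns within children with SNI is not confounded by group.

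Much of this stands and limits the point. It does not remove it, because the Protocol itself fixes levels of any analyte as the primary contrast, states the reading as response, and does not use the pre-incision result to qualify the later comparisons.

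Three stronger readings are tempting but unsupported:
- **That entry-criterion differences will be reported as inflammatory response.** The text shows only that they can be, and that nothing in the plan prevents it.
- **That the hypothesised markers are missing.** CRP and interleukin-6 are examples from research in elderly patients. The hypothesis names no analyte, and the panel content is not given.
- **That the full panel lets a lone inflammatory marker pass only if the groups separate completely.** For a rank test, C(17,5) = 6188, the smallest two-sided p is 2/6188 = 0.00032 and the next 4/6188 = 0.00065, against a first BH step of 0.05/120 = 0.00042. But no test is named for this comparison; Wilcoxon tests appear only for associations with variables such as age and sex. The claim also needs almost no other analyte to differ. Three rejections already raise the threshold to 3 × 0.05/120 = 0.00125, and six to 0.0025.

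**Conclusion.** The point holds as a limited one. The outcome is called inflammatory, the only named assay is described as a CNS-disease panel, and the main contrast compares levels between groups defined by neurological status. Standing differences can therefore enter conclusions about response to surgery. Their size is unknown: the flag rates and counts above rest wholly on the assumed d, share of analytes, independence and correlation, and show what is possible, not what is expected. The problem concerns the SNI-control comparison only. The feasibility and acceptability conclusions are untouched, so the severity is minor to moderate.

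**What to change.** Before the assay is run:

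1. List the panel analytes that form the inflammatory profile, and check whether the cited examples, CRP and interleukin-6, are among them.
2. Give that list its own BH family and volcano plot.
3. Report the remaining analytes separately as exploratory, and say that SNI-control differences in them are not evidence of an inflammatory response to surgery.
4. For the response question, compare between groups the change from timepoint #2 to timepoints #3 and #6, on the log2 scale already used for fold change, alongside the level comparison. Use the pre-incision comparison explicitly when interpreting the later ones.

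The cost is an analyte list, an extra plot and an added contrast on samples already planned. The downsides are that non-inflammatory hits become exploratory, change scores are noisier where pre/post correlation is low, and a child missing either sample drops out of that contrast.
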